1.1.1.4 Assessment of systemic reactogenicity

The occurrence of fever (yes/no, if yes, temperature), fatigue, headache, chills, vomiting, diarrhea, new or worsening muscle pain, new or worsening joint pain is reported by the study subject in a diary for 7 days after dose 1 and dose 2. For individuals who have difficulty completing a diary, study staff will contact the patient on days 2 and 7 after the vaccine dose to collect data by telephone.

Table 2. Systemic Event Grading Scale

	Mild (Grade 1)	Moderate (Grade 2)	Severe (Grade 3)	Potentially Life Threatening (Grade 4)
Vomiting	1-2 times in 24 hours	>2 times in 24 hours	Requires IV hydration	Emergency room visit or hospitalization for hypotensive shock
Diarrhea	2 to 3 loose stools in 24 hours	4 to 5 loose stools in 24 hours	6 or more loose stools in 24 hours	Emergency room visit or hospitalization for severe diarrhea
Headache	Does not interfere with activity	Some interference with activity	Prevents daily routine activity	Emergency room visit or hospitalization for severe headache
Fatigue/ tiredness	Does not interfere with activity	Some interference with activity	Prevents daily routine activity	Emergency room visit or hospitalization for severe fatigue

5.8.4. eDiary

We are looking into the possibility of setting up an eDiary via Alltid öppet, where login with mobile Bank ID is required to access the diary and where study participants can register their local or systemic reactogenicity via the Alltid öppet mobile app. Study staff will have access to this data. This will be offered to study participants who are technically capable and have access to a mobile Bank ID. Alltid öppet is used in routine healthcare to send patient data, which is then entered into the patient's medical records. Similarly, we will manually record data from the eDiary in patients' medical records.

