2.2. Expected results

We expect that some immunosuppressed patients will have a lower degree of immune activation and thereby potentially poorer immunity, compared with

immunocompetent individuals. Individuals who have an absence or partial deficiency in their ability to form antibodies can be expected to develop T cell immunity in certain cases. The degree of immunological response is expected to decrease over time, but it is difficult to predict the duration of a strong immunological response, as we currently lack long-term data. Reactogenicity may be milder in immunosuppressed individuals compared to immunocompetent individuals.

We expect the antibody response to decrease over time, but booster doses and/or new SARS-CoV-2 infections may increase the antibody response, while in some individuals a low/negative antibody response may continue. With the development of new variants, neutralisation capacity may change.

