4.2. Endpoints

Primary endpoint:

- Proportion (95% CI) seroconverting to a positive response to SARS-CoV-2 IgG Serology test after two doses of vaccine, measured 2 weeks after the second vaccine dose.

Secondary endpoints:

- Proportion (95% CI) seroconverting to a positive response to SARS-CoV-2 IgG serology after two doses of vaccine, at 3 months and 6 months after the second vaccine dose.
- Proportion (95% CI) experiencing adverse events, with AE/SAE/SUSAR.
- Number and proportion (95% CI) who experience local reactions and systemic reactions.
- Proportion (95% CI) who receive a new diagnosis of SARS-CoV-2 infection through a positive PCR test.

Exploratory endpoints:

- Proportion (95% CI) seroconverting to a positive response to SARS-CoV-2 IgG serology after two doses of vaccine, at 9 months, 12 months, 18 months, 24 months, 30 months, and 36 months after the second vaccine dose. This may mean that patients in routine healthcare have received one or more additional vaccine doses depending on the recommendations of the Public Health Agency of Sweden.
- A more detailed description of humoral and cellular immune responses at baseline and after vaccinations in blood and saliva at time points immediately before the first vaccine dose (day 0), day 10 after the first dose, immediately before dose 2 on day 21, and 2 weeks, 3 months, 6 months, 9 months, 12 months, 18 months, 24 months, 30 months, and 36 months after the second vaccine dose.
- Prevalence of escape mutations in SARS-CoV-2 sequencing in breakthrough infections.
- Occurrence of development/progression of graft versus host disease in allogeneic stem cell transplant recipients.
- Occurrence of biopsy-verified rejection in solid organ transplant recipients.
- Occurrence of viremia (defined as HIV RNA >50 copies/mL) after vaccination in individuals with HIV infection.
- Change in HIV DNA from study start to 3 and 6 months, 9 months, 12 months, 18 months, 24 months, 30 months, and 36 months after the second vaccine dose in individuals with HIV infection.
- Association between oral and gut microbiome and vaccine response in HIV-infected individuals and controls.

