5.5.3. Reactogenicity (Diary)

Each study participant will be provided with a diary. Study participants will record and rate the severity of symptoms in a diary according to 5.8.3. The evaluation will take place from the day of vaccination until 7 days after the dose, after each vaccine dose.

A reactogenicity event recorded in the diary will not be recorded as an AE unless it meets the criteria for an SAE.

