5.9. Reporting of adverse events

5.9.1. Reporting of adverse events (AE)

- All adverse events should be recorded in a special AE form in the CRF for the period from the day of the first and second vaccine doses until 14 days after each vaccine dose. Exceptions are adverse events that are an expected consequence of the underlying disease, such as worsening of the underlying disease.
- Rationale for the above point: In Phase I and Phase II/III studies of Comirnaty, AEs were collected for the period from informed consent to one month after the second dose. As this has already been studied in approximately 21,000 people with a favorable safety profile, and we do not expect multiple AEs or autoimmune reactions in immunosuppressed individuals, the observation periods are limited to those above. As we expect frequent medical events of a non-serious nature in the majority of the included primary population due to the existing medical condition, such events are excluded from data collection.

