6.3.3. Analyses of secondary endpoints

- Proportion (95% CI) seroconverting to a positive response to SARS-CoV-2 IgG serology after two doses of vaccine, at 3 months and 6 months after the second vaccine dose, measured in the "two-dose vaccine population" compared with the control group.
- Proportion (95% CI) experiencing adverse events, with AE/SAE/SUSAR. Number and proportion (95% CI) experiencing local reactions and systemic reactions are measured in the "Full analysis set population".
- Proportion (95% CI) receiving a new diagnosis of SARS-CoV-2 infection through a positive PCR test is measured in the "Full analysis set population."

- Comparisons are made with the control group.

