6.4. Statistical methods

Continuous variables will be presented with mean and standard deviation [SD] for normally distributed values, and median and interquartile range (IQR) for non-normally distributed values. Categorical variables will be presented as frequency distributions.

Comparisons between patient groups and the control group will be made using the Chi-square test. P-values will be adjusted for multiple comparisons where necessary.

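### Most systemic diary symptoms need not be new or worse than before the dose, so stable background symptoms can count as reactions and distort the comparison with healthy controls.

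*Combined protocol and SAP*

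**What the plan says.** Section 5.8.3, under systemic reactogenicity, asks participants to report fever (with temperature) and these further items: "fatigue, headache, chills, vomiting, diarrhea, new or worsening muscle pain, new or worsening joint pain is reported by the study subject in a diary". The grading table that follows is absolute. For example, fatigue or headache that does not interfere with activity is grade 1, as are two to three loose stools in 24 hours.

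Section 5.5.3 sets the window: "The evaluation will take place from the day of vaccination until 7 days after the dose, after each vaccine dose". It also separates the diary from adverse event recording: "A reactogenicity event recorded in the diary will not be recorded as an AE unless it meets the criteria for an SAE".

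The endpoint is secondary (section 4.2): "Number and proportion (95% CI) who experience local reactions and systemic reactions". Section 6.3.3 adds: "Comparisons are made with the control group". Section 6.4 names the method: "Comparisons between patient groups and the control group will be made using the Chi-square test". No adjustment for symptoms present before the dose is mentioned.

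Two further statements bear on the direction of any error. Section 5.9.1 justifies leaving disease-related events out of adverse event collection: "As we expect frequent medical events of a non-serious nature in the majority of the included primary population due to the existing medical condition". Section 2.2 states the expectation: "Reactogenicity may be milder in immunosuppressed individuals compared to immunocompetent individuals".

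**The concern.** The sentence in section 5.8.3 requires two symptoms to be new or worse and leaves five without that condition. A person with constant mild fatigue can enter grade 1 fatigue after each dose and be counted as having a systemic reaction.

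Such symptoms are unlikely to be equally common in the groups being compared. Patients have chronic disease and often drug treatment, and the protocol expects frequent non-serious events in most of them. Controls are chosen for having no significant co-morbidity (section 5.1.3). Everyone is vaccinated (section 5.1.1), so no group supplies a background rate.

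At stake is the secondary tolerability comparison. An upward shift in patients could look like poorer tolerability, or could cancel a real reduction of the kind the protocol expects.

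**Working it through.** **Step 1: does another part of the plan remove background symptoms?**

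- *Pre-dose record.* The day 0 and day 21 visits (sections 5.2.2 and 5.2.4) list vital signs, medication review and health declaration questions. Neither these lists, Table 2 nor Appendix 1 has a graded pre-dose entry for the diary symptoms. The content of the health declaration is not shown.
- *Causality and disease exception.* The causality categories (section 5.8.2) and the exception for expected consequences of the underlying disease (section 5.9.1) apply to adverse events. Non-serious diary events are not adverse events (section 5.5.3), so neither rule reaches them.
- *Analysis.* Section 6.4 gives a Chi-square test without baseline adjustment.
- *Fever.* It is recorded on occurrence, but temperature is measured before each dose and the dose is postponed at 38 degrees or above, so it is largely protected.

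Nothing in the plan removes a stable symptom from the other five items.

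**Step 2: how large could the effect be?** The plan gives no reactogenicity rate or power, so there is no figure to reproduce. Let v be the proportion with a vaccine-caused systemic symptom and b the proportion who would have a countable symptom in the window anyway. Assuming the two are independent:

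- observed proportion = 1 − (1 − v)(1 − b)
- false excess when v is equal in both groups = (1 − v)(b_patients − b_controls)

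All values of v and b below are assumptions. Control b is 5%.

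| Patient b | False excess, v = 40% | False excess, v = 70% |
|---|---|---|
| 10% | 0.60 × 0.05 = 3 points | 0.30 × 0.05 = 1.5 points |
| 20% | 0.60 × 0.15 = 9 points | 0.30 × 0.15 = 4.5 points |
| 30% | 0.60 × 0.25 = 15 points | 0.30 × 0.25 = 7.5 points |

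Over a wider grid (v = 20–60%, patient b = 5–30%, control b = 0–5%) the false excess runs from 0, when b is equal, to 0.80 × 0.30 = 24 points.

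**Step 3: effect on the test.** Take v = 40% and b = 20% versus 5%. The observed proportions are 1 − 0.6 × 0.8 = 52% and 1 − 0.6 × 0.95 = 43%. With the planned 90 per group and α = 0.05 (two-sided assumed, no multiplicity adjustment), the chance of a falsely significant excess is about 22%. With all 450 patients against 90 controls it is about 34%.

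**Step 4: masking.**

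- True rates 30% in patients and 40% in controls, b = 20% and 5%: observed 1 − 0.7 × 0.8 = 44% and 1 − 0.6 × 0.95 = 43%. The 10-point reduction disappears.
- True rates 30% and 45%, b = 20% and 0%: observed 44% and 45%. Power at 90 versus 90 falls from about 55% to about 3%.

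**The case against.** A reader might infer that chronic symptoms are in fact being counted as vaccine reactions. The documents do not show that. The diary form is not included, section 5.3.3 speaks of participants recording their reactions, and staff review each diary at the 10-day and 2-week contacts. Some participants may leave out long-standing symptoms. This stands, but no rule tells them or the staff to do so, and the grading scale accepts a stable symptom.

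A reader might also infer that nothing about these symptoms is recorded before a dose, or that background symptoms arise almost only in patients. Neither is supported. The health declaration content is unknown. Section 5.9.1 does not name fatigue, headache, chills, vomiting or diarrhoea. Controls include 30 people in the oldest age band and may have headaches or fatigue too. Chills and vomiting are weak candidates for chronic symptoms.

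The size is assumed throughout and shrinks as v rises. Section 3.1 lists several of these reactions as very common, which favours the smaller figures.

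Finally, section 6.1 calls the study descriptive or exploratory, and no reactogenicity hypothesis is powered. Section 2.1 already reports results from two weeks after dose 2, so new diary wording or pre-dose checklists would come too late for participants who have completed their diaries. Both points stand. They limit the consequence and move the remedy to the analysis, but a comparison with controls is still planned.

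**Conclusion.** The point holds in a limited form. As written, the plan permits stable pre-existing symptoms to enter the systemic reaction endpoint, and the patient–control comparison has no step that takes them out. The likely direction is upward in patients, against the expectation in section 2.2. This rests on the inference that background symptoms are commoner in patients than in controls, which sections 5.1.3 and 5.9.1 make plausible but do not quantify.

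The size cannot be derived from the documents. With independence and control b = 5%, the illustrations give 3/9/15 points at v = 40% and 1.5/4.5/7.5 points at v = 70%. If background rates are equal, the false excess is zero. These figures show what the design allows, not a measured bias. A modest analysis change is warranted.

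**What to change.** Add to section 6.3.3, using data already collected:

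1. **A within-person sensitivity analysis.** Count a systemic symptom only if, in the same person and after the same dose, it is present on days 0–2 and absent on days 5–7, or of higher grade on days 0–2 than on days 5–7. For participants followed by telephone, compare day 2 with day 7, the only days they are contacted. The basis is section 3.1, which says reactions usually begin within two days and disappear after 1–2 days.
2. **A restricted comparison.** Compare patients with controls on fever and new or worsening muscle and joint pain only.
3. **A statement on interpretation.** Say that the unadjusted comparison of systemic reactions includes background symptoms.

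For any diary still to be issued, word every systemic item as new or worse than before this dose, and use the same wording in the telephone contacts.

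The cost is one extra table. The within-person contrast misses vaccine reactions that persist beyond day 5 at an unchanged grade, and it still counts an intermittent background symptom that happens to fall only in the first days. It should therefore stand beside the planned analysis, not replace it.

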5.9. Reporting of adverse events

5.9.1. Reporting of adverse events (AE)

- All adverse events should be recorded in a special AE form in the CRF for the period from the day of the first and second vaccine doses until 14 days after each vaccine dose. Exceptions are adverse events that are an expected consequence of the underlying disease, such as worsening of the underlying disease.
- Rationale for the above point: In Phase I and Phase II/III studies of Comirnaty, AEs were collected for the period from informed consent to one month after the second dose. As this has already been studied in approximately 21,000 people with a favorable safety profile, and we do not expect multiple AEs or autoimmune reactions in immunosuppressed individuals, the observation periods are limited to those above. As we expect frequent medical events of a non-serious nature in the majority of the included primary population due to the existing medical condition, such events are excluded from data collection.

5.9.2. Reporting of serious adverse events (SAEs)

- All serious adverse medical events (SAEs) must be noted in the CRF for the period from the first vaccine dose to 6 weeks after the second dose. Exceptions are medical events that are an expected consequence of the underlying disease, such as worsening of the underlying disease.

- SAEs must be reported to the sponsor on a special SAE form within 24 hours of the investigator becoming aware of the SAE. Follow-up information describing the outcome and management of the SAE must be reported as soon as that information is available. The original must be entered in the CRF.
- Rationale for the above points: In Phase I and Phase II/III studies of Comirnaty, SAEs were collected for the period from informed consent to six months after the second dose. As this has already been studied in approximately 21,000 people with a favorable safety profile regarding SAE, and we do not expect multiple SAE or autoimmune reactions in immunosuppressed individuals, the observation periods are limited to those above. As we can expect serious medical events in the majority of the included primary population due to the existing medical condition.

5.9.3. Reporting of suspected, unexpected, serious adverse reactions (SUSAR)

- All suspected, unexpected, serious adverse reactions (SUSARs) should be noted in the CRF for the period from the first vaccine dose to 6 weeks after the second dose. Exceptions are medical events that are an expected consequence of the underlying disease, such as worsening of the underlying disease.
- SUSARs that are fatal or life-threatening shall be reported to the Swedish Medical Products Agency within 7 days of the sponsor becoming aware of the event. Relevant follow-up information shall then be submitted within a further 8 days.
- Other SUSARs shall be reported as soon as possible and no later than 15 days after they have come to the sponsor's attention. The sponsor is responsible for reporting all relevant information about suspected, unforeseen, serious adverse reactions to the Swedish Medical Products Agency.

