4. OBJECTIVE AND ENDPOINTS

4.1. Objective

The primary objective is to investigate the immunological effect of Comirnaty by measuring the incidence of seroconversion (development of antibodies against SARS-CoV-2 upon vaccination in seronegative individuals) after 2 vaccine doses.

Secondary objectives:

- To evaluate safety and tolerability of the given vaccine in the research subjects.
- To measure the incidence of SARS-CoV-2 infection documented by a positive PCR test during the study period.

Exploratory objectives:

- Proportion (95% CI) seroconverting to a positive response to SARS-CoV-2 IgG serology after two doses of vaccine, at 9 months, 12 months, 18 months, 24 months, 30 months, and 36 months after the second vaccine dose. This may mean that patients in routine healthcare have received one or more additional vaccine doses depending on the recommendations of the Public Health Agency of Sweden.
- To investigate the humoral response in more detail and analyze the cellular immune response after the vaccine has been administered.
- To examine the virus genome in breakthrough infections of SARS-CoV-2.
- To evaluate the importance of the oral and intestinal microbiome for vaccine efficacy in HIV-infected individuals.

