5.7. Definitions of adverse events

5.7.1. Incident/Adverse event (AE)

Any incident (AE), or worsening of an existing medical condition in a research subject who has received an investigational drug, regardless of whether it is causally related to the treatment or not, i.e., it may be an adverse and undesirable sign (including an abnormal laboratory finding), symptom, or disease that is temporally associated with the use of an investigational medicinal product, regardless of whether it is related to the investigational medicinal product or not.

However, events that are an expected consequence of the underlying disease, such as worsening of the underlying disease, will not be reported as an AE. This is because we do not expect Comirnaty to affect the progression of the underlying disease.

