5.7.2. Serious incident/Serious adverse event (SAE)

Any incident that:

- results in death
- is life-threatening
- requires hospitalization or prolongs hospitalization
- causes permanent or significant disability or impairment
- results in a congenital injury/malformation
- is serious for other reasons as described below

Medical and scientific judgment should be used to determine whether an event is "serious" and whether it would be reportable in other situations, such as important medical events that may not be directly life-threatening or result in death or hospitalization, but may jeopardise the research subject or may require intervention to prevent one of the other outcomes listed in the definition above. These should also be considered SAEs.

However, events that are an expected consequence of the underlying disease, such as worsening of the underlying disease, will not be reported as SAEs. This is because we do not expect Comirnaty to affect the progression of the underlying disease.

Hospitalization due to day surgery, elective surgery, or admission that was planned before the start of the study for a pre-existing medical condition that has not worsened

is not considered an SAE.

The investigator is responsible for assessing the severity (serious or non-serious). If the incident is considered serious, it should be reported as a serious adverse event (SAE) by the investigator to the sponsor.

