5.7.3. Suspected unexpected serious adverse reactions (SUSAR)

An adverse reaction/event that is serious, unexpected, and suspected to be caused by the treatment, i.e., adverse reactions that are not previously described (in the summary of product characteristics).

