5.8.2. Assessment of causality

The investigator is responsible for determining whether there is a causal relationship between the AE/SAE and the use of an investigational medicinal product. AEs suspected of being related to the investigational medicinal product will be followed up until the research subject has recovered or is well cared for and on the road to recovery. All AEs should be categorized as either probably related, possibly related, or probably unrelated according to the definition below:

- Probable: Clinical event, including abnormal laboratory tests, occurring within a reasonable time after administration of the intervention/study product. Unlikely to be attributable to underlying disease or other drugs.
- Possible: Clinical event, including laboratory tests, occurring within a reasonable time after administration of the intervention/study product. The event can be explained by the investigational medicinal product and its occurrence is reasonable in connection with the use of the investigational medicinal product, but there is insufficient information to establish the connection. The event can be explained by underlying disease or other medicinal products.
- Unlikely: Clinical event, including abnormal laboratory test results, but not reasonable in relation to the use of the intervention/investigational product. The event is unlikely to be related to the intervention/investigational product and can be explained by other drugs or underlying disease.
- Not classifiable: The event cannot be classified due to lack of information or because the event is not verified.

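### The underlying-disease exception has no causality condition, so read literally it leaves possibly vaccine-related serious worsening out of the SAE and SUSAR records

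*Combined protocol and SAP*

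**What the plan says.** All references are to the combined protocol and SAP.

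- **SUSAR definition (5.7.3):** "An adverse reaction/event that is serious, unexpected, and suspected to be caused by the treatment". Unexpected means not already described in the summary of product characteristics.
- **SUSAR recording (5.9.3):** SUSARs are noted in the CRF from the first dose to 6 weeks after the second, followed by "Exceptions are medical events that are an expected consequence of the underlying disease, such as worsening of the underlying disease". Two further bullets set the 7-day and 15-day deadlines for reporting to the agency. They repeat no exception.
- **SAE definition (5.7.2):** "However, events that are an expected consequence of the underlying disease, such as worsening of the underlying disease, will not be reported as SAEs". The reason follows: "This is because we do not expect Comirnaty to affect the progression of the underlying disease".
- **AE and SAE recording (5.9.1, 5.9.2):** the same exception, again without reference to causality. Section 5.9.2 also requires an SAE form to reach the sponsor within 24 hours.
- **AE definition (5.7.1):** it covers an event "or worsening of an existing medical condition in a research subject who has received an investigational drug, regardless of whether it is causally related" to treatment. The next paragraph then says that worsening of the underlying disease is not reported as an AE.
- **Causality (5.8.2):** for the *Possible* category, the product can explain the event, and also "The event can be explained by underlying disease or other medicinal products".
- **Use of the counts:** safety is a secondary objective in 4.1 ("To evaluate safety and tolerability of the given vaccine in the research subjects"). Section 6.3.3 estimates the proportion with AE/SAE/SUSAR in the full analysis set and compares it with the control group. The annual report (5.9.5) summarises SAEs and SUSARs.

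**The concern.** An exception for disease-related events is common in a sick population and reduces noise. Here it does not depend on the causality assessment, and in 5.9.3 it is attached to a class of events that exists only because the vaccine is suspected.

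The stated reason is an expectation that the vaccine does not alter the course of the disease. That is part of what the safety objective is meant to find out, in people whom section 2.1 describes as generally excluded from the earlier trials. An expectation about the answer should not decide which events are counted.

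What is at stake is the reading of the SAE and SUSAR proportions. A low or zero count in patients could reflect the recording rule and not the absence of suspected reactions. The comparison with controls is affected unevenly, because controls have little underlying disease to which the rule could apply.

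**Working it through.** The plan states no figure on this point, so the check is a reading of the rules against each other, followed by a small illustration of direction.

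**1. Can one event satisfy both the SUSAR definition and the exception?**

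| Condition | Where | Serious worsening judged *Possible* |
|---|---|---|
| Serious | 5.7.2 | met |
| Suspected to be caused by the vaccine | 5.7.3, 5.8.2 | met |
| Unexpected, i.e. not in the product summary | 5.7.3 | met if not listed there |
| Expected consequence or worsening of the disease | 5.9.3 | can be met, since *Possible* allows the disease as an explanation |

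Expectedness is judged against the product summary in 5.7.3 and against the disease in 5.9.3, so the last two rows do not exclude each other. Every SUSAR meets the second row by definition. Whatever the exception in 5.9.3 removes is therefore a suspected reaction.

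**2. Where does such an event go?** Under 5.7.2 it is not reported as an SAE, so the 24-hour form in 5.9.2 is not required. Under 5.9.3 it need not be noted as a SUSAR. It then does not enter the 6.3.3 proportions. The agency deadlines run from the sponsor's awareness, and the ordinary route to that awareness has been weakened.

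**3. On which side does it act?** Controls have no immunosuppressive disease or treatment and no significant co-morbidity (5.1.3). Let *c* be the proportion with other counted SAEs, equal in both groups, *w* the proportion of patients with serious worsening, and *f* the share of that worsening left out. Assume no worsening in controls.

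Counted difference = [*c* + *w*(1 − *f*)] − *c* = *w*(1 − *f*)

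| Assumed *w* | *f* = 0 | *f* = 0.5 | *f* = 1 |
|---|---|---|---|
| 5% | 5 points | 2.5 points | 0 |
| 10% | 10 points | 5 points | 0 |

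These rates are assumptions, and *w* includes worsening unrelated to the vaccine. The table shows direction only: the counted excess in patients shrinks toward zero.

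**4. What would a zero count seem to show?** The plan asks for 95% intervals without naming a method. With the exact binomial interval, the upper limit for zero events is 1 − 0.025^(1/n).

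- n = 90 (one patient group): 1 − 0.025^(1/90) = 4.0%
- n = 450 (all patients): 1 − 0.025^(1/450) = 0.8%

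Suppose the true risk of possibly related serious worsening were 1% to 5% (assumption). Then 450 × 0.01 = 4.5 to 450 × 0.05 = 22.5 events would be expected. If all were excepted and nothing else occurred, the pooled limit of 0.8% would appear to rule out that whole range. The single-group limit would appear to rule out only the part above 4.0%.

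**The case against.** Several points on the other side are sound.

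- **Expected consequence may imply attribution first.** The parallel rules in 5.5.5 and 5.5.7 exempt findings that are due to an existing condition, and an investigator could read the exception the same way. That reading is open, but the text does not state it. It names worsening without a causality condition, and under it the exception in 5.9.3 would have nothing to act on.
- **Agency reporting is not exempted.** A reader might infer that SUSARs are withheld from the agency. The documents do not support that, because the exception sits only in the CRF bullet. What stands is the weakened route from site to sponsor.
- **Some worsening is captured elsewhere.** Sections 4.2 and 6.3.4 list graft-versus-host disease, biopsy-verified rejection and HIV viremia. It would be wrong to say that the study loses all vaccine-triggered worsening. But these endpoints are exploratory and outside the SAE/SUSAR counts. The study design overview (Table 2) schedules HIV RNA sampling but no assessment of graft-versus-host disease or rejection. No such endpoint is listed for primary immunodeficiency or CLL.
- **Causality may still be assessed.** A reader might infer that exempted events are never assessed. That is only one reading: 5.7.1 keeps worsening of an existing condition within the AE definition, and 5.8.2 asks for causality of AEs and SAEs. The order of the two steps is simply not stated.
- **Other safety checks exist.** There is no data and safety monitoring committee (5.9.7). However, a steering committee advises on safety (section 9) and safety laboratory tests are scheduled.

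**Conclusion.** The point holds as a defect of wording with a known direction and an unknown size. The exception in 5.9.3 conflicts with the definition in 5.7.3. Read literally together with 5.7.2 and 5.8.2, it leaves possibly related serious worsening out of the SAE/SUSAR records and the 6.3.3 proportions. The bias is toward no excess in patients. This rests on the literal reading and on controls having little disease to except.

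A reader might try to size the loss from 5.9.2, which says that serious events can be expected in the majority of patients. The documents do not support that: the sentence is incomplete, gives no time window and says nothing on relatedness. A serious autoimmune flare in primary immunodeficiency is also not a safe example, because Appendix 1 records autoimmune disease separately from the primary diagnosis. The number of affected events cannot be estimated, and the rates in the illustration are assumptions.

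**What to change.** Reconcile 5.7.1 to 5.7.3, 5.8.2 and 5.9.1 to 5.9.3:

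1. Delete the exception from 5.9.3.
2. In 5.7.1, 5.7.2, 5.9.1 and 5.9.2, limit it to events that the investigator has assessed under 5.8.2 as unlikely to be related to the vaccine.
3. Record and report events assessed as probable, possible or not classifiable, and count them in 6.3.3.
4. For participants whose SAE window closed under the present wording, state the exclusion beside every reported AE/SAE/SUSAR proportion, and do not read a zero as no suspected reactions. Section 2.1 already cites data up to 12 months after the second dose, so rewording alone recovers nothing for the participants behind those data. A review of medical records, with exempted events tabulated by causality and group, could recover part of it.

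The cost is a causality judgement before each exemption and some extra AE/SAE forms. That is not negligible, since 5.9.1 expects frequent non-serious events, but events judged unlikely to be related stay exempt. For those events the comparison with controls remains one-sided, which the report should also say.
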